9.2.2 Reactogenicity

Reactogenicity events are AEs that are common and known to occur following administration of this type of study vaccine. The following Toxicity Grading Scales will be used to grade solicited injection site and systemic (subjective and quantitative) reactions:

Table 4: Injection Site Reactogenicity Grading

Injection Site Reaction	Mild (Grade 1)	Moderate (Grade 2)	Severe (Grade 3)
Pain – experienced without touching the injection site (spontaneous discomfort)	Subject is aware of pain, but it does not interfere with daily activity, and if pain medication is used, it is Over the Counter (OTC) and used for less than 24 hours	Subject is aware of pain; there is interference with daily activity or OTC pain medication is used for more than 24 hours	Subject is aware of pain, and it prevents daily activity or pain requires prescription medication
Tenderness – hurts only when injection site is touched or the arm is moved	The area immediately surrounding the injection site hurts only when touched or with arm motion, and it does not interfere with daily activity	The area immediately surrounding the injection site hurts when touched or with arm motion, and it interferes with daily activity	The area immediately surrounding the injection site hurts when touched or with arm motion, and it prevents daily activity
Pruritus (Itching)	Does not interfere with daily activity	Interferes with daily activity	Prevents daily activity
Ecchymosis (Bruising)*	Does not interfere with daily activity	Interferes with daily activity	Prevents daily activity
Erythema (Redness)*	Does not interfere with daily activity	Interferes with daily activity	Prevents daily activity
Induration (Hardness)/Edema (Swelling)*	Does not interfere with daily activity	Interferes with daily activity	Prevents daily activity

* Will also be measured in mm but size will not be used as halting criteria.

Ecchymosis, erythema and induration (hardness)/edema (swelling) as analyzed by measurement will be graded as follows:

Table 5: Injection Site Reactogenicity Measurements

Injection Site Reaction	Small	Medium	Large
Ecchymosis (Bruising)*	<20 mm	20 mm – 50 mm	>50 mm
Erythema (Redness)*	<20 mm	20 mm – 50 mm	>50 mm
Induration (Hardness)/Edema (Swelling)*	<20 mm	20 mm – 50 mm	>50 mm

* Will not be used as halting criteria.

Table 6: Subjective Systemic Reactogenicity Grading

Systemic (Subjective)	Mild (Grade 1)	Moderate (Grade 2)	Severe (Grade 3)

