9.5 Halting Rules

Additional enrollment and study interventions/administration of study products in this trial will be halted for DSMB review/recommendation if any of the following are reported:

- Any subject experiences ulceration, abscess or necrosis at the injection site that is considered related to study product administration.

- Any 2 or more subjects experience laryngospasm, bronchospasm or anaphylaxis within 1 day after administration of study product that is considered related to study product.
- Three or more subjects experience generalized urticaria (defined as occurring at more than two body parts) within 3 days after administration of study product that is considered related to study product.
- Any subject experiences an SAE after administration of study product that is considered related to study product.
- Any subject experiences acute weakness of limbs and/or cranial nerve innervated muscles (description of potential signal of GBS) after administration of study product.
- Any subject develops a PIMMC after administration of study product.

This trial will also be halted for DSMB review/recommendation if, within 7 days after administration of study vaccination, any of the following occurs:

- 7% or more of subjects (with a minimum of 3 subjects) who received a dose of study vaccine experience the same severe (Grade 3) study vaccine-related injection site reaction. Ecchymosis, erythema and induration (hardness)/edema (swelling) will also be measured in mm but size will not be used as halting criteria.
- 7% or more of subjects (with a minimum of 3 subjects) who received a dose of study vaccine experience the same severe (Grade 3) study vaccine-related subjective systemic reaction, for which the severity (grade) is corroborated by study personnel.
- 7% or more of subjects (with a minimum of 3 subjects) who received a dose of study vaccine experience the same severe (Grade 3) study vaccine-related quantitative systemic reaction.
- 7% or more of subjects (with a minimum of 3 subjects) who received a dose of study vaccine experience the same severe (Grade 3) study vaccine-related clinical safety laboratory AE.

Grading scales for solicited injection site and systemic (subjective and quantitative) reactions are included in [Section 9.2.2](#).

Grading scales for clinical safety laboratory AEs are included in [Section 9.2.3](#).

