#### 9.3.1. Solicited Events and Symptoms

Systemic solicited adverse events will be collected pre-vaccination and systemic and injection site solicited adverse events will be collected approximately 20 minutes post-vaccination and then daily for 7 days after study vaccination. Systemic events include fever, feverishness, fatigue, malaise, myalgia, arthralgia, headache and nausea and the grading scale for systemic events, including quantitative grading for fever is found in [Table 10](#). Injection site events include injection site pruritus, injection site ecchymosis, injection site erythema, injection site induration/swelling, injection site pain and injection site tenderness. Ecchymosis, erythema and induration at the injection site are evaluated using both functional grade and measurement grading scales as defined in [Table 9](#).

When calculating the incidence of solicited events, each subject will be counted once at the highest severity and any repetitions will be ignored. When presenting solicited event summaries, the denominator for percentages will be the number of subjects who received the study vaccination with non-missing data for the event summarized.

The number and percentage of subjects reporting at least one solicited adverse event of any severity will be summarized for each solicited symptom, any systemic symptom, any injection site symptom and any symptom. For each event, the denominator is the number of subjects who received the study vaccination with non-missing data for the specified event. The 95% CI calculated using Clopper-Pearson methodology from a binomial distribution (SAS Proc Freq with a binomial option) will be presented in [Table 50](#).

For each systemic event, each local event, any systemic event, any injection site event, and any solicited event, the maximum severity over 7 days after study vaccination will be summarized for the safety population. The number and percentage of subjects reporting each event will be summarized by the maximum severity, study group, and stratum. For each event the denominator is the number of subjects who received the study vaccination with non-missing data for the specific event. The 95% CI calculated using Clopper-Pearson methodology from a binomial distribution (SAS Proc Freq with a binomial option) will be presented in [Table 51](#).

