## **11. TECHNICAL DETAILS**

SAS version 9.4 or above will be used to generate all tables, figures and listings.

**12. SUMMARY OF CHANGES IN THE CONDUCT OF THE STUDY OR  
PLANNED ANALYSES**

This SAP does not include any changes from the analyses described in the protocol.

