95% CI estimated using Clopper-Pearson exact method  
Severity is the maximum severity reported over all solicited symptoms post dosing for each subject.

**Table 52: Number and Percentage of Subjects Experiencing Solicited Events by Symptom, Severity, Day Post Vaccination, Stratum and Study Group, Safety Population**

Symptom	Severity	Pre-Vac.		Post-Vac.		Day 1		Day 2		Day 3		Day 4		Day 5		Day 6		Day 7		Day 8+	
		n	%	n	%	n	%	n	%	n	%	n	%	n	%	n	%	n	%	n	%
3.75 mcg A/H7N9 (N=X)																					
All Subjects (N*=X)																					
Any Symptom	None																				
	Mild																				
	Moderate																				
	Severe																				
Any Systemic Symptom	None																				
	Mild																				
	Moderate																				
	Severe																				
Fever	None																				
	Mild																				
	Moderate																				
	Severe																				
Feverishness	None																				
	Mild																				
	Moderate																				
	Severe																				
Fatigue	None																				
	Mild																				
	Moderate																				
	Severe																				

Symptom	Severity	Pre-Vac.		Post-Vac.		Day 1		Day 2		Day 3		Day 4		Day 5		Day 6		Day 7		Day 8+	
		n	%	n	%	n	%	n	%	n	%	n	%	n	%	n	%	n	%	n	%
Malaise	None																				
	Mild																				
	Moderate																				
	Severe																				
Myalgia	None																				
	Mild																				
	Moderate																				
	Severe																				
Arthralgia	None																				
	Mild																				
	Moderate																				
	Severe																				
Headache	None																				
	Mild																				
	Moderate																				
	Severe																				
Nausea	None																				
	Mild																				
	Moderate																				
	Severe																				
Any Injection Site Symptom	None																				
	Mild																				
	Moderate																				
	Severe																				
Pain	None																				

Symptom	Severity	Pre-Vac.		Post-Vac.		Day 1		Day 2		Day 3		Day 4		Day 5		Day 6		Day 7		Day 8+	
		n	%	n	%	n	%	n	%	n	%	n	%	n	%	n	%	n	%	n	%
	Mild																				
	Moderate																				
	Severe																				
Tenderness	None																				
	Mild																				
	Moderate																				
	Severe																				
Pruritus	None																				
	Mild																				
	Moderate																				

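### The SAP turns the protocol's size classes for injection site reactions into severity grades and does not say whether they count towards composite maximum severity

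*SAP*

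**What the plan says.** **Protocol, Section 9.2.2.** Table 4 gives ecchymosis, erythema and induration/edema a functional scale. A Grade 1 reaction is one that "does not interfere with daily activity", Grade 2 interferes with activity and Grade 3 prevents it. The footnote on these three reactions reads "Will also be measured in mm but size will not be used as halting criteria". Size then has its own scale, introduced by "Ecchymosis, erythema and induration (hardness)/edema (swelling) as analyzed by measurement will be graded as follows" and titled "Table 5: Injection Site Reactogenicity Measurements". Its classes are Small (under 20 mm), Medium (20 to 50 mm) and Large (over 50 mm). None carries a grade number or a severity word.

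**Protocol, Section 9.5.** The Grade 3 halting rule for injection site reactions repeats the restriction: "Ecchymosis, erythema and induration (hardness)/edema (swelling) will also be measured in mm but size will not be used as halting criteria".

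**SAP, Section 9.3.1 and Table 9.** The text says "Ecchymosis, erythema and induration at the injection site are evaluated using both functional grade and measurement grading scales as defined in" Table 9. That table heads the size columns Small (Grade 1), Medium (Grade 2) and Large (Grade 3). The same section calls for maximum severity for any injection site event and any solicited event, without naming the scale to be used.

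**SAP, Tables 51 and 52.** Each of the three reactions has two rows, one functional and one marked as a measurement. Both have the levels None, Mild, Moderate and Severe. The note to Table 51 states: "Severity is the maximum severity reported over all solicited symptoms post dosing for each subject".

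**SAP, Section 12.** "This SAP does not include any changes from the analyses described in the protocol".

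**The concern.** In the protocol, Large and Severe mean different things: one is millimetres, the other is loss of function. The SAP gives them one vocabulary. A reader of Table 51 would then meet Severe entries that the protocol's functional scale calls Mild, in a document that says nothing has changed.

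The composite rows are the larger worry. A reader looks first at the rows for any injection site symptom and any symptom. If size counts there, large but non-limiting reactions raise the Severe share. Protocol Section 2.3.1 expects redness and swelling to be more frequent and more severe with AS03, so any such rise would probably fall mainly on the adjuvanted groups and widen the apparent severity gap. If size does not count, the note is wrong. As drafted, two programmers could produce different composite severity counts from the same data.

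**Working it through.** The plan states no figure on this point, so the check is a comparison of the tables followed by an illustration.

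**Worked cases.** Take a subject whose only solicited symptom is erythema.

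| Erythema | Protocol Table 4 | Protocol Table 5 | SAP functional row | SAP measurement row | Composite, functional grades only | Composite, all rows |
|---|---|---|---|---|---|---|
| 60 mm, activity not affected | Mild (Grade 1) | Large | Mild | Severe | Mild | Severe |
| 30 mm, activity not affected | Mild (Grade 1) | Medium | Mild | Moderate | Mild | Moderate |
| 15 mm, prevents activity | Severe (Grade 3) | Small | Severe | Mild | Severe | Severe |

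Three things follow.

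1. The disagreement between the two rows comes directly from SAP Tables 9, 51 and 52. It needs no interpretation.
2. A maximum can only move up when rows are added. Including size can therefore raise composite severity but never lower it.
3. Every reaction in the table is at least Mild on the functional scale, so none versus any is the same whichever scale is used.

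**Illustration of scale.** Neither document gives a rate of reactions over 50 mm. Assume that a proportion L of subjects has such a reaction without limitation of activity, and that nobody has any other severe event. The expected number counted as Severe through size alone is n × L. The chance of at least one is 1 − (1 − L)^n. The second formula also underlies SAP Table 5: at 1% it gives 39.5% for n = 50 and 87.9% for n = 210, against the printed 39 and 87.

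| Assumed L | Expected in a group of 50 | Expected in 210 AS03 recipients | Chance of at least one in 50 |
|---|---|---|---|
| 1% | 50 × 0.01 = 0.5 | 210 × 0.01 = 2.1 | 1 − 0.99^50 = 39.5% |
| 5% | 50 × 0.05 = 2.5 | 210 × 0.05 = 10.5 | 1 − 0.95^50 = 92.3% |
| 10% | 50 × 0.10 = 5.0 | 210 × 0.10 = 21 | 1 − 0.90^50 = 99.5% |

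With functional grades only, every expected count here is 0. The values of L are assumptions, chosen to show a range.

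**The case against.** The strongest reply is that the protocol itself grades size. Section 9.2.2 presents Table 5 among its grading scales and says that measured reactions will be graded by it. Its only express limit is on halting, and SAP Section 6.6.1 respects that by deferring to Protocol Section 9.5. The protocol does not forbid grade numbers on size, and it does not say which scale should drive a composite. This stands in part. A separate size display is legitimate, and basing composites on function is a recommendation consistent with Table 4, not a rule that the protocol states. It does not explain why size should borrow the words Mild, Moderate and Severe while Section 12 reports no change.

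The second reply concerns the note. A reader might infer that the SAP definitely feeds size into the composite rows. No SAP sentence says so. Section 9.3.1 names six injection site events and treats measurement as a second way of evaluating three of them. Nor can the note be literal for the whole table, because a maximum over all symptoms would give every single-symptom row the same counts. The parallel note to Table 52 has no such pooling wording. This stands: what can be shown is an unresolved rule whose plain wording includes size.

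Third, functional and measurement rows are printed side by side, so a careful reader can see where the Severe entries in the single-symptom rows come from. That is true of those rows. It does not help with a composite row, which merges its sources.

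**Conclusion.** The mismatch in labels is certain. Followed as written, the SAP prints a non-limiting reaction over 50 mm as Severe in the measurement rows of Tables 51 and 52. Entry into the composite rows is possible on the wording of the Table 51 note and unresolved elsewhere; Figure 27, which plots maximum injection site severity by day, has the same gap.

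The reach is limited to the severity distribution. A reader might infer that the primary safety endpoint is distorted. The documents do not support that. The endpoint is occurrence, Protocol Section 11.6.2 dichotomises solicited events as none against any severity, and the reactions at issue already count as Mild. SAP Table 50 and the solicited rows of SAP Table 48 carry no severity levels. The functional rows and the halting rules are also untouched.

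The size of the effect cannot be derived from the documents. Any statement that the severe rate would rise from one percentage to another rests on assumed rates, including those in the illustration above. The expectation of a larger effect with AS03 rests on the protocol's description of the adjuvant, which gives a direction but no rate of reactions over 50 mm.

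**What to change.** 1. Restore Small, Medium and Large, without grade numbers, in SAP Table 9, and use None, Small, Medium and Large in the measurement rows of Tables 51 and 52. Table 50 has no severity levels and needs no relabelling.
2. State in SAP Section 9.3.1 that maximum severity in the composite rows of Tables 51 and 52 and in Figure 27 uses the functional grades of Protocol Table 4. Show size as a separate block.
3. Correct the Table 51 note: severity is the maximum over post-vaccination days within each symptom, and the maximum over symptoms applies to the composite rows only.
4. If the sponsor wants size to count, declare it in SAP Section 12 and show composite severity both with and without size.

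The cost is wording in the table shells and one derivation rule. No data collection changes. It should be settled before unblinding, by when Protocol Section 11.6 requires the SAP to be final.

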**14.3.1.2 Unsolicited Adverse Events**

**Table 53: Number and Percentage of Subjects Experiencing Unsolicited Adverse Events with 95% Confidence Intervals by MedDRA System Organ Class and Preferred Term, Stratum and Study Group, Safety Population**

MedDRA System Organ Class	MedDRA Preferred Term	2013 A/H7N9 IIV + MF59 (N=X)		2013 A/H7N9 IIV + AS03 (N=X)		2013 A/H7N9 IIV 15 mcg or 45 mcg unadjuvanted (N=X)		2013 A/H7N9 IIV with MF59/AS03 then 2013 A/H7N9 IIV 15 mcg (N=X)		A/H7 IIV Naïve (N=X)		All Subjects (N=X)	
		n	% (95% CI)	n	% (95% CI)	n	% (95% CI)	n	% (95% CI)	n	% (95% CI)	n	% (95% CI)
3.75 mcg A/H7N9 IIV													
Any SOC	Any PT	x	xx (xx-xx)	x	xx (xx-xx)	x	xx (xx-xx)	x	xx (xx-xx)	x	xx (xx-xx)	x	xx (xx-xx)
[SOC 1]	Any PT												
	[PT 1]												
	[PT 2]												
[SOC 2]	Any PT												
	[PT 1]												
	[PT 2]												
3.75 mcg A/H7N9 IIV + AS03													
Any SOC	Any PT	x	xx (xx-xx)	x	xx (xx-xx)	x	xx (xx-xx)	x	xx (xx-xx)	x	xx (xx-xx)	x	xx (xx-xx)
[SOC 1]	Any PT												
	[PT 1]												
	[PT 2]												
[SOC 2]	Any PT												
	[PT 1]												
	[PT 2]												
All Subjects													

MedDRA System Organ Class	MedDRA Preferred Term	2013 A/H7N9 IIV + MF59 (N=X)		2013 A/H7N9 IIV + AS03 (N=X)		2013 A/H7N9 IIV 15 mcg or 45 mcg unadjuvanted (N=X)		2013 A/H7N9 IIV with MF59/AS03 then 2013 A/H7N9 IIV 15 mcg (N=X)		A/H7 IIV Naïve (N=X)		All Subjects (N=X)	
		n	% (95% CI)	n	% (95% CI)	n	% (95% CI)	n	% (95% CI)	n	% (95% CI)	n	% (95% CI)
Any SOC	Any PT	x	xx (xx-xx)	x	xx (xx-xx)	x	xx (xx-xx)	x	xx (xx-xx)	x	xx (xx-xx)	x	xx (xx-xx)
[SOC 1]	Any PT												
	[PT 1]												
	[PT 2]												
[SOC 2]	Any PT												
	[PT 1]												
	[PT 2]												

Notes: N = Number of subjects in the safety population in the given stratum; n = number of subjects with reported event.  
A subject is only counted once per PT.

**Table 54: Number and Percentage of Subjects Experiencing Unsolicited Adverse Events by MedDRA System Organ Class and Preferred Term, Maximum Severity, Relationship, Stratum and Study Group, Safety Population**

MedDRA System Organ Class	MedDRA Preferred Term	Any Incidence		Severity a						Relationship to Vaccination b			
				Mild		Moderate		Severe		Not Related		Related	
		n	%	n	%	n	%	n	%	n	%	n	%
3.75 mcg A/H7N9 (N=X)													
All Subjects (N*=X)													
Any SOC	Any PT	x	xx	x	xx	x	xx	x	xx	x	xx	x	xx
[SOC 1]	Any PT												
	[PT 1]												
	[PT 2]												
[SOC 2]	Any PT												
	[PT 1]												
	[PT 2]												
[repeat for Strata 1 - 5]													
[repeat for 3.75 mcg A/H7N9 IIV + AS03 (N=X) and All Subjects (N=X)]													
Notes: N = Number of subjects in the safety population in the given study group; N* = Number of subjects in the safety population in the given study group and stratum; n = number of subjects with reported event.													
a For severity, a subject is counted once per preferred term and is summarized according to their highest severity.													
b For relationship, a subject is only counted once per preferred term and is summarized according to their closest relationship.													

**Table 55: Number and Percentage of Subjects Experiencing Non-Serious Related Unsolicited Adverse Events by MedDRA System Organ Class and Preferred Term, Maximum Severity, Stratum and Study Group, Safety Population**

MedDRA System Organ Class	MedDRA Preferred Term	Any Incidence		Severity a					
				Mild		Moderate		Severe	
		n	%	n	%	n	%	n	%
3.75 mcg A/H7N9 (N=X)									
All Subjects (N*=X)									
Any SOC	Any PT	x	xx	x	xx	x	xx	x	xx
[SOC 1]	Any PT	x	xx	x	xx	x	xx	x	xx
	[PT 1]								
	[PT 2]								
[SOC 2]	Any PT								
	[PT 1]								
	[PT 2]								
[repeat for Strata 1 - 5]									
[repeat for 3.75 mcg A/H7N9 IIV + AS03 (N=X) and All Subjects (N=X)]									
Notes: N = Number of subjects in the safety population in the given study group; N* = Number of subjects in the safety population in the given study group and stratum; n = number of subjects with reported event.									
a For severity, a subject is counted once per preferred term and is summarized according to their highest severity.									

**Table 56: Number and Percentage of Subjects Experiencing Unsolicited Adverse Events Within 21 Days Post Study Vaccination by MedDRA System Organ Class and Preferred Term, Day Post Vaccination, Stratum and Study Group, Safety Population**

		2013 A/H7N9 IIV + MF59 (N=X)				2013 A/H7N9 IIV + AS03 (N=X)				2013 A/H7N9 IIV 15 mcg or 45 mcg unadjuvanted (N=X)				2013 A/H7N9 IIV with MF59/AS03 then 2013 A/H7N9 IIV 15 mcg (N=X)				A/H7 IIV Naïve (N=X)				All Subjects (N=X)			
		Day 1-8 Post Vac		Day 9-22 Post Vac		Day 1-8 Post Vac		Day 9-22 Post Vac		Day 1-8 Post Vac		Day 9-22 Post Vac		Day 1-8 Post Vac		Day 9-22 Post Vac		Day 1-8 Post Vac		Day 9-22 Post Vac		Day 1-8 Post Vac		Day 9-22 Post Vac	
MedDRA System Organ Class	MedDRA Preferred Term	n	%	n	%	n	%	n	%	n	%	n	%	n	%	n	%	n	%	n	%	n	%	n	%
3.75 mcg A/H7N9																									
Any SOC	Any PT	x	xx	x	xx	x	xx	x	xx	x	xx	x	xx	x	xx	x	xx	x	xx	x	xx	x	xx	x	xx
[SOC 1]	Any PT																								
	[PT 1]																								
	[PT 2]																								
[SOC 2]	Any PT																								
	[PT 1]																								
	[PT 2]																								
[repeat for 3.75 mcg A/H7N9 IIV + AS03 and All Subjects]																									
Notes: N = Number of subjects in the safety population in the given stratum; n = number of subjects with reported event. For each time period, a subject is only counted once per PT.																									

**Table 57: Number and Percentage of Subjects Experiencing Non-Serious, Related Unsolicited Adverse Events Within 21 Days Post Vaccination by MedDRA System Organ Class and Preferred Term, Study Vaccination, Stratum and Study Group, Safety Population**

		2013 A/H7N9 IIV + MF59 (N=X)				2013 A/H7N9 IIV + AS03 (N=X)				2013 A/H7N9 IIV 15 mcg or 45 mcg unadjuvanted (N=X)				2013 A/H7N9 IIV with MF59/AS03 then 2013 A/H7N9 IIV 15 mcg (N=X)				A/H7 IIV Naïve (N=X)				All Subjects (N=X)			
		Day 1-8 Post Vac		Day 9-22 Post Vac		Day 1-8 Post Vac		Day 9-22 Post Vac		Day 1-8 Post Vac		Day 9-22 Post Vac		Day 1-8 Post Vac		Day 9-22 Post Vac		Day 1-8 Post Vac		Day 9-22 Post Vac		Day 1-8 Post Vac		Day 9-22 Post Vac	
MedDRA System Organ Class	MedDRA Preferred Term	n	%	n	%	n	%	n	%	n	%	n	%	n	%	n	%	n	%	n	%	n	%	n	%
3.75 mcg A/H7N9																									
Any SOC	Any PT	x	xx	x	xx	x	xx	x	xx	x	xx	x	xx	x	xx	x	xx	x	xx	x	xx	x	xx	x	xx
[SOC 1]	Any PT																								
	[PT 1]																								
	[PT 2]																								
[SOC 2]	Any PT																								
	[PT 1]																								
	[PT 2]																								
[repeat for 3.75 mcg A/H7N9 IIV + AS03 and All Subjects]																									
Notes: N = Number of subjects in the safety population in the given stratum; n = number of subjects with reported event. For each time period, a subject is only counted once per PT.																									

**Table 58: Number of Unsolicited Adverse Events by MedDRA System Organ Class and Preferred Term, Day Post Vaccination, Stratum and Study Group, Safety Population**

		2013 A/H7N9 IIV + MF59 (N=X)		2013 A/H7N9 IIV + AS03 (N=X)		2013 A/H7N9 IIV 15 mcg or 45 mcg unadjuvanted (N=X)		2013 A/H7N9 IIV with MF59/AS03 then 2013 A/H7N9 IIV 15 mcg (N=X)		A/H7 IIV Naïve (N=X)		All Subjects (N=X)	
		Day 1-8 Post Vac	Day 9-22 Post Vac	Day 1-8 Post Vac	Day 9-22 Post Vac	Day 1-8 Post Vac	Day 9-22 Post Vac	Day 1-8 Post Vac	Day 9-22 Post Vac	Day 1-8 Post Vac	Day 9-22 Post Vac	Day 1-8 Post Vac	Day 9-22 Post Vac
MedDRA System Organ Class	MedDRA Preferred Term	Events	Events	Events	Events	Events	Events	Events	Events	Events	Events	Events	Events
3.75 mcg A/H7N9													
Any SOC	Any PT	x	x	x	x	x	x	x	x	x	x		
[SOC 1]	Any PT												
	[PT 1]												
	[PT 2]												
[SOC 2]	Any PT												
	[PT 1]												
	[PT 2]												
[repeat for 3.75 mcg A/H7N9 IIV + AS03 and All Subjects]													
Notes: N = Number of subjects in the safety population in the given stratum.													

